## **Progression-free Survival (PFS) - Secondary Endpoint**

Progression-free survival will be calculated as the number of days from the date of the first dose of CO-1686 to the date of disease progression or death due to any cause + 1. Patients without a documented event of disease progression will be censored on the date of their last adequate tumor assessment (i.e., radiologic assessment) or date of first dose of study drug if no tumor assessments have been performed. Any valid tumor measurements are considered adequate for efficacy assessments. Patients with measurable disease at baseline will have disease progression determined by RECIST Version 1.1 criteria.

The Kaplan-Meier methodology will be used to summarize progression-free survival. The 25th, 50th (median), and 75th percentiles will be presented.

PFS will be evaluated by the investigator and by IRR.

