#### **3.4.1.1 Tumor Responses Associated with CO-1686**

[figure not shown]
Although the data are immature, there is evidence of activity for CO-1686 across the therapeutic doses for patients confirmed as T790M-positive by central testing ([Figure 2](#)) with 14 of 22 patients achieving a partial response per RECIST as of the data cut-off date. The ORR in this group of patients is approximately 64% ([Table 5](#)) and the disease control rate is approximately 91%. Some of the responses have occurred too recently to allow confirmation. Of the 9 responses that have had the opportunity to be confirmed, 7 (78%) have indeed been confirmed. As shown in [Figure 2](#), 10 of the 14 patients (71%) who achieved a partial response had discontinued from EGFR-directed therapy immediately prior to enrolling in Clinical Study CO-1686-008. Median PFS has not been reached in the T790M-positive subgroup, but will exceed 120 days ([Figure 3](#)).

**Figure 2: Best Response for Target Lesions in Centrally Confirmed T790M-positive Patients****Table 5: Best Response, Objective Response, and Disease Control Rate in T790M-positive Patients**

	900 mg BID FB (N = 9)	500 mg BID HBr (N = 4)	625 mg BID HBr (N = 4)	750 mg BID HBr (N = 4)	1000 mg BID HBr (N = 3)	Overall (N = 24)
Best Response a						
PR	7 (77.8%)	2 (50.0%)	2 (50.0%)	0 (0.0%)	3 (100.0%)	14 (58.3%)
SD	2 (22.2%)	0 (0.0%)	0 (0.0%)	4 (100.0%)	0 (0.0%)	6 (25.0%)
PD	0 (0.0%)	2 (50.0%)	0 (0.0%)	0 (0.0%)	0 (0.0%)	2 (8.3%)
End of Cycle 2 scan not yet reached	0 (0.0%)	0 (0.0%)	2 (50.0%)	0 (0.0%)	0 (0.0%)	2 (8.3%)
Objective Response a, b (CR, PR)						
	7 (87.5%)	2 (50.0%)	2 (100.0%)	0 (0.0%)	3 (100.0%)	14 (63.6%)
Disease Control Rate a, b (CR, PR, SD)						
	9 (100.0%)	2 (50.0%)	2 (100.0%)	4 (100.0%)	3 (100.0%)	20 (90.9%)

a Data shown are for patients with measurable disease at baseline

b Percentage based on patients with non-missing best response

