### **9.8.2 Efficacy Evaluations**

#### 9.8.2.1 Tumor Assessments

Tumor assessments will be performed at screening; at the end of Cycles 2, 4, and 6 (between Days 14 and 21); every 3 cycles after Cycle 6 (between Days 14 and 21); and at the End of Treatment visit. Tumor response will be interpreted using RECIST Version 1.1 ([Appendix A](#)).

If an initial CR or PR is noted at Cycle 7 or beyond, confirmatory scans must be performed 4 to 6 weeks later. In the case of SD, follow-up measurements must have met the SD criteria at least once after study entry at a minimum interval of no less than 6 to 8 weeks.

Patients who continue treatment with CO-1686 post-progression should continue to be scanned according to the protocol until they discontinue from the study.

Tumor assessments should consist of clinical examination and appropriate imaging techniques (preferably CT scans of the chest, abdomen, and pelvis with appropriate slice thickness per RECIST Version 1.1); other studies (MRI and X-ray) may be performed if required. The same methods used to detect lesions at baseline are to be used to follow the same lesions throughout the clinical study.

Brain imaging (MRI/CT) is required at baseline. Patients with known brain metastases and/or brain lesions detected at baseline are required to repeat brain imaging as part of the follow-up tumor assessments. The same methods used to detect brain lesions at baseline are to be used to follow the same lesions throughout the clinical study.

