## **Overall Survival (OS) - Secondary Endpoint**

Overall survival (OS) will be calculated as 1+ the number of days from the first dose of study drug to death due to any cause. Patients without a documented date of death will be censored on the date the patient was last known to be alive.

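### The PFS censoring sentence makes no exception for death, so it contradicts the PFS event definition and, taken literally, would censor deaths without documented progression and overstate PFS

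*Protocol*

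**What the plan says.** The PFS paragraph of Protocol Section 11.2.4.2 measures time from first dose "to the date of disease progression or death due to any cause + 1". The next sentence reads "Patients without a documented event of disease progression will be censored on the date of their last adequate tumor assessment", and continues "or date of first dose of study drug if no tumor assessments have been performed". The paragraph also states "The Kaplan-Meier methodology will be used to summarize progression-free survival" and "PFS will be evaluated by the investigator and by IRR", so one rule serves both assessors.

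The OS paragraph in the same section handles censoring differently: "Patients without a documented date of death will be censored on the date the patient was last known to be alive".

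SAP Section 2.2.2 keeps PFS among the Phase 2 secondary objectives. SAP Section 10.2 does not list it as a secondary variable, and SAP Section 15, item 4, leaves PFS analyses out because the study is still ongoing.

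**The concern.** The event has two parts, progression or death, but the trigger for censoring looks at only one of them. A patient who dies with no documented progression satisfies the first sentence (event on the date of death) and the second (censored at the last scan, or at first dose if never scanned). The two instructions cannot both be carried out.

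Such deaths are foreseeable:

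- Treatment may stop for clinical progression (Protocol 5.1.3), and Appendix A recognises symptomatic deterioration without objective progression.
- Scheduled scans end with the End of Treatment visit (9.8.2.1), while survival follow-up goes on about every two months (5.4, 9.7).
- The SAP expects deaths before the first post-baseline scan. It adds them to the tumor-evaluable population (Section 4) and gives them their own ORR category (Section 15, item 1). PFS has no matching rule.
- PFS by IRR is the more exposed. If the investigator calls progression, treatment stops and the IRR does not confirm it, a later death falls under the censoring sentence.

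Every patient receives CO-1686 in an open-label design, so there is no comparator arm in which the same bias would appear, and readers will use the absolute PFS estimate.

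**Working it through.** **1. Does any other text settle the conflict?**

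- Protocol synopsis (Efficacy Analysis) and Section 11.2.1: name Kaplan-Meier only; no PFS censoring rule.
- Protocol 11.2.4.2, OS: the trigger (no recorded death) matches the event (death). The PFS trigger does not match its event.
- SAP Section 3: Kaplan-Meier and counts of events and censored patients; no PFS rule.
- SAP Sections 10.2 and 15: PFS absent or left out.

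The PFS paragraph is therefore the only PFS rule in either document. The documents give no target median, event count or power for PFS, so there is no stated figure to reproduce.

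**2. Direction, in ten hypothetical patients.** Days since first dose: deaths without progression at 20, 60 and 80; progressions at 84, 126, 126, 189, 189 and 252; one patient censored at 300.

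- Deaths as events: Kaplan-Meier steps are 0.9, 0.8, 0.7, 0.6 (day 84), 0.4 (day 126). Median 126 + 1 = 127 days.
- Deaths censored at the last scan (days 0, 42, 42): seven remain at risk at day 84. Steps are 6/7 = 0.857 (day 84), 4/7 = 0.571 (day 126), 2/7 = 0.286 (day 189). Median 189 + 1 = 190 days.

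Here 3 of 9 events are deaths, which is a high share; the example shows the mechanism, not the likely size.

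**3. Size, analytic.** Assume exponential times, true median m, and a share f of first events that are deaths without progression. The total hazard is ln 2/m and the progression part is (1 − f) ln 2/m. Censoring the deaths leaves only the progression part, so the median becomes m/(1 − f). The only PFS level in the documents is "Median PFS has not been reached in the T790M-positive subgroup, but will exceed 120 days" (Protocol 3.4.1.1, immature Phase 1 data). With m = 120 as a low-end illustration: 120/0.95 = 126 days, 120/0.90 = 133, 120/0.80 = 150.

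**4. Size, simulated on the protocol schedule.** Scans are "at the end of Cycles 2, 4, and 6 (between Days 14 and 21); every 3 cycles after Cycle 6". With 21-day cycles that is about days 42, 84 and 126, then every 63 days. Assumed: exponential times, progression recorded at the next scan, administrative cut-off uniform on 120 to 480 days, 200,000 patients per setting. Each pair is death as event, then death censored.

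| True median (days) | Observed death share | 6-month PFS | Kaplan-Meier median (days) |
|---|---|---|---|
| 120 | 5.9% | 0.471, 0.498 | 126.0, 126.9 |
| 120 | 11.6% | 0.465, 0.518 | 126.0, 183.9 |
| 120 | 22.7% | 0.448, 0.556 | 125.9, 185.9 |
| 180 | 5.8% | 0.608, 0.630 | 189.1, 246.1 |
| 180 | 11.3% | 0.600, 0.645 | 188.9, 247.3 |
| 180 | 22.3% | 0.585, 0.677 | 188.7, 250.1 |
| 270 | 5.6% | 0.716, 0.734 | 310.5, 312.4 |
| 270 | 11.3% | 0.712, 0.748 | 310.1, 314.3 |
| 270 | 22.2% | 0.699, 0.771 | 300.6, 374.2 |

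The 6-month gain runs from 1.8 points (0.734 − 0.716) to 10.8 points (0.556 − 0.448). In three settings the median moves by 1 to 4 days. In the other six it moves by 57 to 74 days, about one 63-day scan interval.

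A similar simulation with a 6-month true median gives these 12-month PFS values:

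- 5.6% deaths: 0.299 to 0.323, +2.4 points
- 11.1% deaths: 0.298 to 0.344, +4.6 points
- 16.4% deaths: 0.298 to 0.365, +6.7 points
- 21.7% deaths: 0.292 to 0.385, +9.3 points

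The exact gains shift somewhat with the follow-up assumed.

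**The case against.** The strongest reply is that the intent is plain. The event sentence names death; Section 11.2.1 reports patients with events and censored patients as separate groups; and the literal censoring reading would empty the death clause for everyone who dies without documented progression. A careful programmer would probably count these deaths. That stands. A reader might infer that the plan sets out to censor deaths, and the documents do not support that: what they contain is two conflicting sentences.

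A reader might also infer that the analyses for the NDA and MAA are biased. They are not affected through this route, because the SAP that describes them leaves PFS out. PFS is a descriptive secondary endpoint with no test or threshold. Under Amendment 8 enrolment is closed and scans no longer go to central review (Appendix D). A clinical study report is still planned (Protocol 13.9), so a later PFS report is possible but not specified.

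The size is also open to challenge. Death share and median are assumptions. Because progression is dated only at scans, the median moves in steps, and a small change in the curve can carry it to the next scan or leave it where it was. The simulation has scans continuing until progression or death, so it does not represent patients who stop for toxicity, have no further scans and die much later. How to treat long scan gaps and new anticancer therapy is a separate analysis choice; it does not remove the contradiction.

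**Conclusion.** The wording conflict is certain and should be corrected. Followed literally, the censoring sentence turns deaths without documented progression into censored observations, and the resulting bias is upward: PFS was higher in every setting tried. For deaths making up 5% to 22% of first events, 12-month PFS rises by about 2 to 9 points, and the median either hardly changes or moves by about one scan interval. These figures rest on exponential times, the protocol scan schedule, and an assumed death share and median; they illustrate and do not predict. A reader might take them as evidence of a large known bias, which the documents cannot support, since they give neither input. The consequence is confined to a future PFS report by investigator or by IRR.

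**What to change.** Replace the censoring sentence in the PFS paragraph of Protocol Section 11.2.4.2 with wording to this effect: a patient who is alive with no documented progression is censored at the last adequate tumor assessment, or at first dose if none was done; a death with no earlier documented progression is an event on the day of death. Use the same text for investigator and IRR PFS, and carry it into any SAP version that reports PFS.

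The cost is one sentence and no new data. Reported PFS may be less favourable than under the literal censoring rule.

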### **11.2.5 Pharmacokinetic Analyses – Secondary Endpoint**

As a primary endpoint in Phase 1 and a secondary endpoint in Phase 2 of the study, PK parameters will be determined using noncompartmental methods. AUC from Time 0 to the last

observation will be calculated using the trapezoid rule. The  $k_{el}$  will be calculated using log-linear regression on the terminal part of the concentration time curve. The terminal half-life and the AUC from the last observation to infinity will be calculated from the estimated  $k_{el}$ . Other parameters to be determined are  $C_{max}$ ,  $T_{max}$ ,  $V_{ss}/F$ , and  $Cl/F$ .

As a secondary endpoint in Phase 1, the effect of food on PK parameters including, but not limited to,  $C_{max}$  and AUC, will be compared using analysis of variance (ANOVA) techniques.

As a secondary endpoint in Phase 2, additional plasma samples will be collected on Day 15 from a minimum of three patients enrolled at the RP2D. Individual pooled plasma samples, one from each of these patients, will be prepared using the method proposed by Hamilton. The pooled plasma samples will be further processed before being analyzed by high-performance liquid chromatography coupled in-line with ultraviolet spectrophotometric and tandem mass spectrometric detection (HPLC-UV-MS/MS).

A specific population PK data analysis plan will be developed and will outline the detailed approach to data handling, model development and diagnostics, individual model parameter estimation, exploration of covariate effects, and final model evaluation techniques.

### **11.2.6 Patient Reported Outcomes – Secondary Endpoint**

Patient reported outcome questionnaires, the EORTC QLQ C30 and LC13 and the Dermatology Life Quality Index will be summarized with descriptive statistics on observed data for all three PRO instruments and their subscales. Specifically, the domain and item scores from the EORTC-QLQ-C30 (global health status; physical, role, emotional, cognitive, and social functioning; fatigue, nausea and vomiting, and pain symptoms; dyspnea; insomnia; appetite loss; constipation; diarrhea; and financial difficulties), from the lung cancer module (dyspnea, coughing, hemoptysis, sore mouth, dysphagia, peripheral neuropathy, alopecia, pain in chest, pain in arm or shoulder, and pain in other parts) and from the DLQI (DLQI total score, daily activities, leisure, personal relationships, symptoms and feelings, treatment, and work/school) will be summarized using descriptive statistics (i.e., N, mean, StDev, median, Q1, Q3, min, and max) at each scheduled assessment point by phase and overall. Additionally, change from baseline in the domain and item scores at the time of each assessment will be summarized.

Mean changes from baseline (including standard deviation bars) in EORTC-QLQ-C30 lung cancer module symptom scores and DLQI domain scores will be plotted at each assessment point. At each assessment point on the x axis the number of patients completing the assessment for each treatment group should be listed. The y axis should encompass only the range of values reported by patients in the study (as opposed to the full range of the scale).

Additional details on the analysis of the patient reported outcome data will be provided in the statistical analysis plan.

### **11.2.7 Relationship Between PK and QTc – Secondary Endpoint**

In Phase 1 patients and in a subset of Phase 2 patients participating in full PK profiling, an endpoint of the study will be to examine the relationship between the concentration of oral CO-1686 (PK) and potential changes in QTc. A linear and nonlinear mixed effect modeling approach will be used to quantify the relationship between the plasma concentration and the  $\Delta QTc$  baseline-adjusted difference in QTc interval. Plots of the mean QT/QTc versus drug concentrations and a concentration-QT variables correlation will be explored.

### **11.2.8 Time to Treatment Failure - Exploratory Endpoint**

The time to treatment failure will be computed as 1+ the number of days from the first dose of study drug to the last dose of study drug.

The subgroup of patients that continue receiving study drug past an event of disease progression will be summarized separately.

### **11.2.9 Concordance of T790M in Tumor versus Blood – Exploratory Endpoint**

An exploratory pharmacodynamic endpoint is the detection and quantification of mutant EGFR cell-free DNA in blood collected at baseline and with every tumor assessment. The presence of the T790M mutation at baseline and subsequent time points will be presented both with frequencies and percentages. In addition, the relationship between T790M detected in tumor compared with that detected in blood, and urine where applicable, will be explored. This will involve determining the sensitivity, specificity, positive and negative predictive values with 95% confidence intervals (CIs) of blood with respect to tumor assuming that EGFR mutational status in tumor is a true reflection of tumor biology. Blood collected at these time points may also be assessed for cell-free DNA related to biomarkers of response or resistance to EGFR-targeted therapy.

### **11.2.10 Safety Analyses**

The safety analyses will be performed using the safety population (all patients who have received at least one dose of CO-1686).

#### **11.2.10.1 Extent of Exposure**

The following will be summarized by dose group using descriptive statistics:

- Number of patients dosed in Phase 1 (Dose-escalation Period and Treatment-extension Period and RP2D Exploratory cohort), and in Phase 2
- Number of patients at each dose group, average dose amount, total cumulative dose (Phase 1 and 2)
- Number of cycles initiated (Phase 1 and 2)
- Number of dose reductions/delays (Phase 1 and 2)
- Number of dose interruptions (Phase 1 and 2)
- Duration of exposure (Phase 1 and 2)

The number of patients at each dose group or study phase will be summarized with frequencies and percentages; the average dose, total cumulative dose, and duration of exposure will be summarized with descriptive statistics and frequency counts for relevant categories. The number of cycles initiated will be investigated by summarizing the number of cycles started by each patient in each period. The number of patients with at least one dose reduction/delay or interruption will be summarized with frequencies and percentages.

#### **11.2.10.2 Adverse Events**

AE coding will be performed using the Medical Dictionary for Drug Regulatory Activities, Version 13.0 or greater. The severity of the toxicities will be graded according to the NCI

CTCAE Version 4.0 whenever possible. Treatment-emergent AEs are defined as AEs with an onset date on or after the date of first dose of CO-1686 until the date of the last CO-1686 dose plus 28 days. AEs will be considered treatment-emergent if all or part of the date of onset of the AE is missing and it cannot be determined if the AE meets the definition for treatment-emergent.

The number and percentage of patients who experienced treatment-emergent AEs for each system organ class and preferred term will be presented by dose group. Multiple instances of the treatment-emergent AEs in each system organ class and multiple occurrences of the same preferred term are counted only once per patient. The number and percentage of patients with at least one treatment-emergent AE will also be summarized by dose group.

Separate tables will present the following by dose group and study phase:

- All treatment-emergent AEs
- Treatment-emergent AEs by CTCAE grade
- Grade 3 or greater treatment-emergent AEs
- Treatment-related, treatment-emergent AEs
- Dose-limiting toxicity AEs
- Serious treatment-emergent AEs
- Serious treatment-related AEs
- Treatment-emergent AEs with an outcome of death
- Treatment-emergent AEs leading to discontinuation of oral CO-1686
- Treatment-emergent AEs resulting in interruption or reduction/delay of CO-1686

The incidence of treatment-emergent AEs will be summarized by relationship to oral CO-1686 using “treatment-related” and “not treatment-related” categories. The category of treatment-related is defined as a relationship of Possible/Probable, Definite, or Missing. If a patient experiences multiple occurrences of the same AE with different relationship categories, the patient will be counted once as a relationship category of treatment-related.

If a patient experiences multiple occurrences of the same AE with different intensity toxicity grades, the patient will be counted once for the maximum (most severe) toxicity grade. AEs with a missing intensity will be presented in the summary table with a toxicity grade of “Missing.” For each toxicity grade, the number and percentage of patients with at least one treatment-emergent AE of the given grade will be summarized.

Non-treatment-emergent AEs (pretreatment and posttreatment) will be presented in the by-patient data listings.

#### 11.2.10.3 Clinical Laboratory Evaluations

Clinical laboratory evaluations include the continuous variables for hematology, serum chemistry, and urinalysis. Laboratory values will be presented in Systeme International units. The baseline laboratory value will be defined as the last value prior to or on the day of the first dose of oral CO-1686. The on-treatment period will be defined as the day after the first dose of oral CO-1686 to 28 days after the last dose of CO-1686. Laboratory values collected during the

on-treatment period will be included in the summary tables. The laboratory values collected after the on-treatment period will only be presented in the data listings.

The summary of laboratory data will include descriptive statistics (N, mean, standard deviation, minimum, median, and maximum) of the maximum, minimum, and last value during the treatment period by dose group and study phase. Summaries using descriptive statistics of the change from baseline to the maximum, minimum, and last value during the on-treatment period will also be given by dose group and study phase. Supporting laboratory data including normal ranges and abnormal laboratory flags will be provided using by-patient listings. Separate listings will be produced for clinically significant laboratory abnormalities (i.e., those that meet Grade 3 or 4 criteria according to CTCAE Version 4.0) by dose group.

#### 11.2.10.4 Vital Sign Measurements

The baseline vital sign measurement will be defined as the last value prior to or on the day of the first dose of CO-1686. The on-treatment period will be defined as the day after the first dose of CO-1686 to 28 days after the last dose of CO-1686. Vital sign measurements collected during the on-treatment period will be included in the summary tables. The vital sign measurements collected after the on-treatment period will only be presented in the data listings.

The summary of vital sign data will include descriptive statistics (N, mean, standard deviation, minimum, median, and maximum) of the maximum, minimum, and last value during the on-treatment period by dose group and study phase. Summaries using descriptive statistics of the change from baseline to the maximum, minimum, and last value during the on-treatment period will also be given by dose group.

